## 3.5 Framework

Both PROMOTE and PREVENT are fully powered superiority trials; both trials seek to evaluate superiority of the personalised intervention compared with both usual care and a standard active intervention. The SAP from this point onwards refers to both PROMOTE and PREVENT as they are identical in their analysis methods; the only difference between the two is in the choice of which of an identical set of outcome measures constitutes the primary outcome measure.

## 3.6 Statistical interim analysis and stopping guidelines

No interim analyses will be performed for efficacy or harms. As the intervention is considered to be low risk to participants, there are no formal guidelines for early termination of the trial due to potential for harm to participants. All adverse and serious adverse events will be reported to the TSC and DMEC for their consideration; if the TSC and DMEC consider that there is sufficient cumulative evidence of harm to participants due to the intervention(s), the trial will be discontinued. Also, there are no guidelines for early termination due to futility (inability to achieve statistical significance for a treatment effect) or achieving significant results prior to full data analysis.

## 3.7 Timing of analyses

We anticipate performing all analysis following final database lock, when all follow-up data (up to and including 12-month follow-up) has been entered and cleaned. However, in the event that follow-up takes longer than expected (for example, if the sample size is increased due to higher loss to follow-up than was accounted for in the power calculation), it may be necessary to perform analysis of data up to 3-month follow-up and then perform analyses that include 12-month follow-up data at a later time.

Participants' timing throughout the trial will be relative to their trial allocation and randomisation, which will occur immediately following collection of baseline data.

## 3.8 Timing of outcome assessments

Follow-up timepoints are at 1-, 3- and 12-month follow-up (3-month follow-up is the primary timepoint). Each participant will have a scheduled follow-up date for each of the three follow-up timepoints, to be allocated on date of randomisation. Data collection will be sought within a 14-day window (within 7 days before or after the scheduled date) for 1-month follow-up. Data collection will be sought within a 28-day window (within 14 days before or after the scheduled date) for 3- and 12-month follow-up. Data collected outside this window will not be included in the primary analysis, although sensitivity analyses including all collected data will be performed.

## 3.9 Allocation masking

Participants will not be specifically informed of their treatment allocation. Participants will be informed prior to consenting to participate that they may be randomly selected to receive additional support and education in mental health and wellbeing via the app. Therefore, it is reasonable to assume that participants allocated to the usual care intervention who do not receive any support or information vie the app will be able to deduce that they are in a control arm, although this should be mitigated to some extent by the cohort trial design. Similarly, participants allocated to either of the two active interventions will be aware that they have been selected to receive additional support and education, and may be able to determine whether they are in the personalised intervention arm or the standard intervention arm. The issue of differential participant awareness of intervention arm will be considered when interpreting the results.

All outcome data is participant reported and will be collected via the website with no direct contact between participants and researchers. Contact between a participant and researcher would only occur if the researcher's support is required for concerns about risk of harm to the participant or for technical support with use of the app or as an additional attempt to obtain primary outcome data. Thus, there is the possibility for inadvertent unblinding of the researcher if such contact occurs. Any cases of researcher unblinding will be logged. There is provision for data collection to be conducted by telephone if a participant is unwilling or unable to use the website; such instances are anticipated to be rare, and in such cases, data collection will be performed by a blinded researcher. Data collected by telephone (as opposed to via the website, which is standard) will be recorded as such. There may be extremely rare instances where data collection by telephone is performed by an unblinded researcher, and such cases will be recorded as such.

Following database lock on completion of 3-month data collection, the database will be made available to the trial statistician with masked treatment allocation. The final database with completed 12-month follow-up data will be made available to the trial statistician following database lock; at this point the trial statistician will be aware of allocations.

### 3.10 Trial flow of participant events

The flow of participant events within the trial is set out in discrete steps below.

- 1. Potential participant visits trial website, expresses interest in the trial and provides baseline screening data to allow eligibility (including age and country of residence) to be assessed.
- 2. The potential participant will be invited to provide data on the emotional competence measurements that will enable the cohort member to be allocated to either PROMOTE or PREVENT.
- 3. If the potential participant is eligible, the potential participant will be invited to consent to join the top level recruitment cohort (2142 participants) who will provide self-monitoring data via the app and to participate in the appropriate trial within the cohort. (If the potential participant is not eligible due to previous or current mental health conditions, signposting to sources of support will be provided.)
- 4. The cohort member will be allocated to PROMOTE or PREVENT.
- 5. If cohort member consents to participate in the allocated trial, the participant will be randomised to treatment allocation and if allocated to the personalised intervention, the appropriate components will be selected based on the data provided previously.
- 6. Access to the app for intervention delivery is provided as soon as the participant has been randomly allocated to intervention.
- 7. Follow-up at 1 month.
- 8. Follow-up at 3 months.
- 9. Follow-up at 12 months.

## 4. Statistical principles

### 4.1 Confidence intervals and p-values

All inferential analyses will be reported using 95% confidence intervals and p-values, with the threshold for statistical significance set at 0.05. No formal testing for multiple comparisons will be performed (whether for the multiple comparisons across the three trial arms or for multiple comparisons across the primary and secondary outcomes); the p-values for the primary outcomes will be interpreted first, and the p-values for the secondary outcomes will be interpreted in the light of the overall results. Global p-values will be used where there are two or more contrasts being examined in the same model; 95% confidence intervals will be used to interpret individual contrasts.

#### 4.2 Intervention adherence and protocol deviations

For participants receiving the active interventions, we will descriptively report data on intervention adherence. Protocol deviations will be reported narratively within the trial report, with descriptive analysis only if required. With regard to treatment allocation, there is no possibility of a participant accessing one of the other active interventions, i.e. other than the allocated intervention.

## 4.3 Analysis populations

The primary analysis will on the intention to treat (ITT) basis (i.e. participants will be included in the analyses according to their randomised allocation) and will include observed data only). There is no possibility for a participant to receive an active intervention if this was not the participant's randomised allocation. The only possibility for a participant failing to receive the randomised intervention is if the participant did not adhere. An `as treated' analysis is not required as there is no possibility for a participant to receive a non-allocated intervention.

## 5. Trial population

## 5.1 Screening data

Screening data for age, gender and country will be available for participants who are eligible to enter the trial (either PROMOTE or PREVENT) but do not consent to participate, and will be reported descriptively.

## 5.2 Eligibility

Participants will be eligible for the overall cohort if they are (i) aged between 16–22; (ii) resident in the UK, Germany, Spain or Belgium; and (iii) have no past history of mental health disorders or current mental health disorders. Further eligibility criteria are set out in Protocol version 1.3. Participants will be eligible for PROMOTE if they are at lower risk of mental health problems as determined by their responses to eight measures of emotional competence; participants will be eligible for PREVENT if they are at higher risk of mental health problems as determined by their responses to these measures (full details of the deterministic allocation method to either PROMOTE or PREVENT are set out elsewhere: Trial selection, randomisation, selection of emotional competence intervention components document).

## 5.3 Recruitment

It is anticipated that each country will recruit an average of 14 potential participants (eligible for PROMOTE/PREVENT and consenting to participate) per week. Recruitment will take place over a period of 9 to 12 months within the 4 countries, therefore anticipated recruitment is 2240 to 2912 participants ((14 x 4 x 40) to (14 x 4 x52)), exceeding the required number for the top level cohort (2142 potential participants).

Outlines of the proposed CONSORT flow diagrams are set out below (Figures 1 and 2).

#### 5.4 Withdrawal and loss to follow-up

If a participant formally withdraws from the trial (i.e. a participant contacts the trial team to request withdrawal from the trial), the trial team will ask the participant if the participant is willing to continue to provide outcome data, even if the participant no longer wishes to continue to adhere to the randomised allocation. Also, the trial team will ask the participant if the participant is willing to allow the trial to use the data already provided. If the participant is not willing to allow the trial to use the data already provided. If the participant is not willing to allow the trial to use the data will be permanently deleted in accordance with GDPR. The time of withdrawal from the trial will be noted; a reason for trial withdrawal will also be requested. Participants will receive reminders to complete outcome measures at 1-, 3- and 12-month follow-up. Participants who do not complete outcome measures for a specified follow-up will be requested to provide follow-up data for subsequent follow-up timepoints, unless they have contacted the trial team to formally withdraw from the trial.

Participants found to be ineligible following randomisation will be withdrawn from the trial; the numbers of ineligible withdrawn participants will be reported by trial arm with reason for ineligibility.

## 5.5 Baseline participant characteristics

Participant characteristics at baseline will be reported descriptively by treatment arm (Table A.1). Baseline characteristics will be compared across treatment arms to assess balance; for those characteristics that appear unbalanced (using guidelines of a difference across arms  $\geq$  1 SD for continuous variables or  $\geq$ 10 percentage points for categorical variables) across arms will be included as a covariate in analyses (if thought predictive of outcome and at the discretion of the statistician and chief investigator).

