10.3.2 Primary analysis

The primary outcomes (WEMWBS (ECoWeB-PROMOTE); PHQ-9 (ECoWeB-PREVENT) and secondary outcomes will be compared at 3-month follow-up. The primary and secondary continuous outcomes will be reported descriptively (mean and standard deviation (SD)) and inferential comparisons will be reported between the three treatment contrasts ((1) usual practice plus personalised digital self-help EC vs. usual practice alone; (2) usual practice plus non-personalised automated digital CBT self-help vs. usual practice alone; (3) usual practice plus personalised digital self-help EC vs. usual practice alone; (3) usual practice plus personalised digital self-help EC vs. usual practice plus non-personalised automated digital CBT self-help) using linear modelling. All analyses will be based on an intention to treat principle (i.e. according to original allocation irrespective of intervention adherence) and will include participants with complete outcome data at 3-month follow-up, and will adjust for baseline outcome score (where relevant) and minimisation variables (age, gender, country). Furthermore, we will adjust for any baseline participant characteristics that are substantively unbalanced at baseline (defined as a difference ≥ 10 percentage points across categories for a categorical variable, or a difference in means >1 SD for continuous variables), and if the characteristic is thought to be predictive of outcome. Binary secondary outcomes (occurrence of major depressive disorder; generalized anxiety disorder) will be reported as proportions and analysed used logistic regression.

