## 6.3 Analysis methods

All continuous outcomes will be reported descriptively (mean, SD) at all follow-up timepoints. Inferential analyses The primary analyses for the primary and continuous secondary outcomes will use linear regression models with adjustment for baseline score, age (as a continuous variable rather than the dichotomised minimisation variable), country, and any other participant characteristics observed at baseline to be unbalanced across treatment arms (meeting the criteria set out in Section 5.5). The primary follow-up time will be at 3 months; analysis of 12-month follow-up data will also be performed using the same approach. The primary analyses will be based on an intention to treat (ITT) approach (i.e. all participants will be included in the analyses according to their randomised allocation) and will use observed data only.

As a secondary analysis, we will perform repeated measures analyses (using a mixed effects linear regression model with a random effect on participant) for primary and secondary continuous outcomes, including data from participants with observed data for at least one of the three follow-up timepoints. Analyses will be performed to compare both active interventions with usual care, and to compare the personalised active intervention with the standard active intervention. A fixed effect interaction between timepoint and trial arm will be used to evaluate differential treatment effects across timepoints. Adjustments for baseline covariates will be made as for the primary analysis regression models; baseline score will be included as a covariate. Binary outcome measures will be analysed using logistic regression models with adjustments for covariates as above.

The primary analyses will use only the data collected during the time window. The amount of such data will be determined, with the possibility of performing a sensitivity analysis should the amount of data collected outside the time window be substantive. These analyses will be performed using observed data for the ITT population (i.e. according to initial random allocation). No formal adjustments of p-values for multiple testing will be performed; the results for the primary outcome will be interpreted first and the results of the secondary outcomes will then be interpreted in the light of multiple testing. The results of all descriptive and inferential analyses for the primary and secondary continuous outcomes are set out in Tables A.4–A.10.

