# 11. Appendices

| Characteristic  | Personalised digital self-
help + usual care (N=X) | Non-personalised digital
self-help +usual care
(N=X) | Usual care (N=x) |
|---|---|--|------------------|
| Age (years); mean (SD),
median [25 th centile; 75 th
centile] |   |  |                  |
| Age (years)   |   |  |                  |
| 16–17   |   |  |                  |
| 18-22   |   |  |                  |
| Gender  |   |  |                  |
| Male  |   |  |                  |
| Female  |   |  |                  |
| Both  |   |  |                  |
| Neither   |   |  |                  |
| Country   |   |  |                  |
| UK  |   |  |                  |
| Germany   |   |  |                  |
| Spain   |   |  |                  |
| Belgium   |   |  |                  |
| Ethnic group (tbc)  |   |  |                  |
|   |   |  |                  |
| Education (tbc)   |   |  |                  |
| Occupation (tbc)  |   |  |                  |
| · · ·   |   |  |                  |
| Post-randomisation  |   |  |                  |
| App outage disruption   |   |  |                  |
| Disruption prior 1-month  |   |  |                  |
| follow-up   |   |  |                  |
| Disruption prior to 3-  |   |  |                  |
| month follow-up   |   |  |                  |
| Disruption prior to 12-
month follow-up  |   |  |                  |
| No disruption   |   |  |                  |

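### Covariates can enter the primary model on observed baseline imbalance and at discretion, so the model is not fully fixed in advance; the effect is small and falls mainly on PREVENT

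*SAP*

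**What the plan says.** SAP 5.5 reports baseline characteristics by arm in Table A.1 and compares the arms. Its guideline for imbalance is a difference of at least "1 SD for continuous variables" or at least "10 percentage points for categorical variables". A characteristic that meets it becomes a covariate if it is judged prognostic and "at the discretion of the statistician and chief investigator".

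SAP 6.3 carries this into the primary linear regression, which adjusts for baseline score, age, country and "any other participant characteristics observed at baseline to be unbalanced across treatment arms". The same covariates are carried into the 12-month, CACE, imputed-data and adverse-event models (SAP 6.3, 6.5, 6.6, 6.10).

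Protocol 10.3.2 has a similar rule, with three differences:

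- Its continuous threshold is "a difference in means >1 SD for continuous variables", a strict inequality.
- It requires adjustment "if the characteristic is thought to be predictive of outcome" and has no discretion clause.
- Its fixed adjustment set includes gender, which SAP 6.3 leaves out although SAP 3.3 minimises on it.

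Protocol 10.3 says that the SAP's details take precedence. Neither document lists candidate covariates, and ethnic group, education and occupation are still to be confirmed in Table A.1.

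**The concern.** In a properly randomised trial a baseline difference between arms is chance. What earns a covariate its place is its relation to the outcome, and that can be judged before any data are seen. This rule makes chance imbalance the gate and leaves the prognostic judgement for later, with two people's discretion on top.

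Two things are at stake. First, the primary model cannot be written down before the data are examined. Secondly, the rule gives no dependable gain in precision. Related baseline scales (PHQ-9 and GAD-7 in PROMOTE, WEMWBS and GAD-7 in PREVENT) are collected from everyone but would enter only through a threshold that randomisation will not produce. A sociodemographic category of unknown prognostic value could enter by luck.

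**Working it through.** **Inputs.** Per-arm numbers come from SAP 3.4 and 6.9. The plan's own sizes reproduce with n = 2(1.960 + 1.282)² × (SD/difference)²:

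- PROMOTE: 2 × 10.51 × (11.3/3.0)² gives 299 (stated 300); 300/0.6 = 500 per arm.
- PREVENT, with the protocol's difference of 2.59: 2 × 10.51 × (5.4/2.59)² gives 92 (stated 93); 93/0.6 = 155 per arm. The SAP's printed 5.9 would give 18, which is a separate inconsistency.
- PREVENT as expected from the initial cohort: 642/3 = 214 per arm.
- Revised total of 3599 at the 70:30 split: 3599 × 0.7/3 ≈ 840 per arm in PROMOTE and 3599 × 0.3/3 ≈ 360 in PREVENT.

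**Continuous limb.** The standard error of a standardised mean difference between two arms is √(2/n), so 1 SD equals 1/√(2/n) standard errors. At 155 per arm, √(2/155) = 0.114 and 1/0.114 = 8.8, with a two-sided chance for one pair of about 10⁻¹⁸. Larger arms make it rarer still.

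**Categorical limb.** The standard error of a difference in proportions is √(2p(1−p)/n). At p = 0.5 and n = 155 it is √(0.5/155) = 0.0568, so 10 points is 0.10/0.0568 = 1.76 standard errors. The last two columns give the exact binomial chance that at least one of the three pairs of arms differs by 10 points or more under pure chance. The documents give no prevalences for ethnic group, education or occupation, so 20% and 50% are assumptions.

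| Trial and size per arm | 1 SD in standard errors | 20% prevalence | 50% prevalence |
|---|---|---|---|
| PREVENT, required: 155 | 8.8 | 7.1% | 18.3% |
| PREVENT, initially expected: 214 | 10.3 | 2.5% | 9.4% |
| PREVENT, revised: 360 | 13.4 | 0.3% | 2.2% |
| PROMOTE, required: 500 | 15.8 | 0.03% | 0.5% |
| PROMOTE, revised: 840 | 20.5 | about 0 | 0.01% |

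At 10% prevalence the PREVENT figures fall to 0.9%, 0.2% and 0.003%.

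**Several variables together.** For illustration, take three independent variables with assumed category splits of 70/10/10/10, 40/30/20/10 and 50/30/20. By simulation, at least one meets the threshold in about 58% of trials at 155 per arm, 32% at 214, 7% at 360, 1.5% at 500 and 0.03% at 840.

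**Which participants are compared.** These figures take balance as judged in everyone randomised, the natural reading of SAP 5.5. The SAP does not say so outright, and the primary analysis uses observed data only. With 40% attrition, 360 per arm becomes 360 × 0.6 = 216, and the chance returns to roughly the 214 row.

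**The case against.** The strongest reply is that the rule is bounded and does little harm. It has numeric guidelines and already asks for a prognostic link. Baseline outcome score, age and country are in the SAP model regardless. Country, gender and age band are minimised, so the rule bites mainly on three sociodemographic variables. A limb that never fires leaves that part of the model fixed; indeed the only continuous variable shown in Table A.1 is age, which is adjusted for anyway. The gain from further baseline scales is not quantified, and the documents give no correlations from which to estimate it. All of this stands, and it limits the size of the point.

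A reader might infer that the discretion could be used to favour an arm. The documents do not support that for the primary analysis: SAP 7.1 has the 3-month inferential analyses run by a masked statistician, with allocations revealed only after results are presented. Masking does not, however, fix the covariate list before outcomes are seen. Nor does it cover 12 months, where SAP 3.9 says the statistician will know the allocations and SAP 6.3 applies the same approach.

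A reader might also infer that the rule fires often in both trials. At the revised sizes it is uncommon in PREVENT and practically absent in PROMOTE.

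**Conclusion.** The point holds as a weakness of pre-specification, mainly in PREVENT. The text lets the primary model depend on observed imbalance and on discretion. The continuous limb is inert at every planned size, so it never brings in a prognostic baseline scale. The categorical limb acts only by chance: per binary category, about 7–18% at PREVENT's required size, 2.5–9.4% at its initially expected size, 0.3–2.2% at the revised size, and 0.5% or less in PROMOTE. These rates rest on assumed prevalences of 20–50%, a 70:30 split and balance judged in all randomised participants.

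It would be wrong to conclude that the rule biases the treatment estimate. Under random allocation it does not do so by itself. The loss is a model that is not fixed in advance, plus precision of unknown amount. That justifies a change because the change is nearly free, not because the primary result is in danger.

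**What to change.** In SAP 5.5 and 6.3, delete the imbalance rule and the discretion clause, and align Protocol 10.3.2. Before any outcome data are seen, fix one covariate set for the primary model in both trials:

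- baseline score of the outcome being analysed;
- all minimisation factors: age, country and gender, which restores agreement with Protocol 10.3.2;
- baseline WEMWBS, PHQ-9 and GAD-7 as pre-specified prognostic covariates.

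Use the same set wherever the SAP refers back to the primary model's covariates. Report baseline imbalance descriptively only; any model adjusted for an observed imbalance should be labelled a sensitivity analysis.

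The cost is SAP wording. Every variable is already collected at baseline (Protocol 3.7). Relative to SAP 6.3 the primary model gains at most five coefficients (three for the four gender categories and two for the extra scales), against 3 × 93 = 279 analysed participants even at PREVENT's minimum size.
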